The enzyme adenosine deaminase (ADA) has an essential role in the intracellular degradation of purine nucleosides derived from DNA breakdown. In ADA deficient cells, deoxyadenosine is metabolized by deoxycytidine kinase (dCk), resulting in increased cellular concentrations of deoxyadenosine mono-, di-, and tri-phosphates (dAMP, dADP, and dATP), that are toxic to the cells.²⁰ 2-chlorodeoxyadenosine (2-CdA, cladribine) is a purine analog resistant to ADA but not to dCk. This results in accumulation of chlorinated deoxyadenosine nucleotides that may be eventually incorporated into the DNA of dividing cells, which results in induction of arrest in the S phase of the cell cycle,²¹ and activation of the apoptotic pathway. However, in contrast with conventional antimetabolites, 2-CdA is extremely toxic to mature, non-dividing lymphocytes. High concentrations of deoxynucleotides might interfere with the repair of DNA breaks, thus initiating the process of programmed cell death.²² In children, 2-CdA has mainly been used in the treatment of AML, where responses of up to 59% are obtained as a single agent.²³ Normal mature lymphocytes and monocytes express high levels of dCk.²⁴ In vitro studies have shown that 2-CdA is a highly selective anti-monocyte agent, which causes decreased monocyte function and viability and decreased IL-6 secretion.²⁵ Because tissue histiocytes are derived from the same stem cells as circulating monocytes, 2-CdA has been investigated for the treatment of patients with histiocytic disorders. Excellent clinical responses, with an overall response rate of 82% have been reported in adults with recurrent LCH.²⁶ In children, the role of 2-CdA has been explored in two scenarios.

CONFIDENTIAL

This document is confidential. Do not disclose or use except as authorized.

- a) For patients with low-risk disease reactivation, cladribine has shown to induce responses in > 90% of the patients, although further reactivations still occur.^{16,27-29} One additional benefit of cladribine is its effect on CNS disease (a common complication of LCH).^{30,31} A major limitation with the use of cladribine is its limitation to a short treatment course; more than 4 or 6 courses of treatment are associated with prolonged myelosuppression, causing a clinical picture similar to myelodysplasia.

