10 ADVERSE EVENT REPORTING REQUIREMENTS

All adverse events that occur after the initial dose of study treatment, during treatment, or within 30 days of the last study intervention need to be captured. Adverse events will be followed for 30 days after the last study intervention if a participant discontinues protocol treatment early. All AEs need to be followed until resolution.

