13.3 Study Design/Endpoints

The primary endpoint within each stratum will be the proportion of responders. A responder is defined as an eligible, evaluable participant who achieves either complete resolution or regression of disease, i.e., their disease gets "Better" per section 9.1, as the best overall response at any time up to and including the End of Cycle 2 assessment, which must be completed on Day 28 of Cycle 2 +/- 7 days, and must be completed prior to starting Cycle 3.

Secondary endpoints are:

- a) Progression-free survival (PFS), where time to event for PFS is the time from study enrollment until the time of first occurrence of new lesions, progressive disease, or death from any cause, or until last contact if no event occurs;
- b) Overall survival (OS), calculated as the time from enrollment until death or last contact;

CONFIDENTIAL

This document is confidential. Do not disclose or use except as authorized.

- c) Feasibility, which is assessed by the proportion of patients who experience a toxicity-event. Participants who have clofarabine stopped because of toxicity concerns will be considered to have experienced a toxicity-event. Otherwise, participants who complete therapy or who are removed from protocol therapy for reasons related to disease progression, second malignancy or death unrelated to protocol therapy will be considered to have successfully tolerated treatment; and,
- d) The proportion of participants reporting grades 3-4 toxicity, for each CTCAE v4.0 toxicity code.

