13.5 Monitoring Rules

The study will be referred to the DSMC for review of dosing and toxicity at the first occurrence of a toxic death.

A Simon's two-stage group sequential design will be used to determine if there is sufficient evidence of efficacy to warrant further investigation of clofarabine.

Rule A - Two-stage stopping rule for response in Stratum 1

Stage 1: Accrue 13 evaluable participants. If 7 or fewer respond, then there is insufficient evidence to support further study of clofarabine in this cohort, and the study will be closed to further accrual. We would also close the trial if it became apparent prior to the accrual of all 13 that we would never achieve the 8 responders. If 8 or more out of 13 are responders, then proceed to stage 2.

Stage 2: A total of 20 evaluable patients will be studied. If 13 or fewer respond, then there is insufficient evidence to support further study of clofarabine in this cohort. If 14 or more are responders, then there is sufficient evidence to warrant further investigation of clofarabine within this cohort.

This rule has 91% power to detect a 27% difference (53% under the null to 80% under the alternative), with $\alpha = 0.093$. If the response rates were actually higher, there would be even greater power to detect a 27% difference, for example 63% versus 90%.

Rules for monitoring for toxicity associated with chemotherapy

The study will be monitored to ensure the therapy can be delivered as planned ('chemotherapy feasibility'). Toxicities will be graded according to CTCAE version 4.0. Unacceptable toxicity will be defined as grade 5 toxicity and Grade 3 or 4 non-hematological toxicity that are possibly, probably, or definitely related to Clofarabine, with the specific exceptions of the following Grade 3 toxicities: anorexia, weight loss, nausea, vomiting, fatigue, mucositis, diarrhea, fever, electrolyte/metabolic abnormalities, menorrhagia, and

CONFIDENTIAL

This document is confidential. Do not disclose or use except as authorized.

infection. Because all patients, regardless of stratum, receive the same treatment with the standard dose of clofarabine (25 mg/m²/d), the stopping rule for toxicity will be applied to the overall cohort, i.e., combining Stratum 1 and Stratum 2. The toxicity monitoring rule will be applied to the first 25 evaluable participants, as this will provide sufficient evidence of safety/feasibility for the balance of the trial's accrual.

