Rule B – Three-stage stopping rule for toxicity events

Stage 1: Accrue 7 evaluable participants. If at any time 2 or more participants experience a toxicity-event, enrollment will be suspended for DSMB review of dosage modifications or stopping the trial. If 1 or fewer have a toxicity-event, then proceed to stage 2.

Stage 2: Accrue an additional 8 evaluable participants for a total of 15. If at any time 3 or more participants experience a toxicity-event, enrollment will be suspended for DSMB review of dosage modifications or stopping the trial. If 2 or fewer have a toxicity-event, then proceed to stage 3.

Stage 3: Accrue an additional 10 evaluable participants for a total of 25. If 7 or more participants experience a toxicity-event, then there is insufficient evidence to support chemotherapy feasibility. If 6 or fewer have a toxicity-event, then there is sufficient evidence that the therapy can be delivered as planned, and this evidence supports continuation until the accrual goal for this trial is reached.

If all 25 participants are evaluated and the true toxicity-event rate is 5%, the therapy will be considered tolerable with a probability of 0.94. If all 25 participants are evaluated and true toxicity-event rate is 30%, the therapy will be considered tolerable with a probability of 0.1.

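### Rule B has two unlinked event definitions, and under 13.3(c) a treatment-related death after completed therapy is scored as tolerated while one between cycles has no category

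*Combined protocol and SAP*

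**What the plan says.** Section 13.3(c) defines the feasibility endpoint. The event is: "Participants who have clofarabine stopped because of toxicity concerns will be considered to have experienced a toxicity-event". Everyone else is handled by the next sentence, which begins "Otherwise, participants who complete therapy or who are removed from protocol therapy for reasons related to disease progression, second malignancy" and ends "second malignancy or death unrelated to protocol therapy will be considered to have successfully tolerated treatment". Completing therapy is not defined.

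Section 13.5 introduces the toxicity monitoring with a different concept: "Unacceptable toxicity will be defined as grade 5 toxicity and Grade 3 or 4 non-hematological toxicity that are possibly, probably, or definitely related to Clofarabine", followed by a list of exempt grade 3 toxicities. It also has a separate trigger: "The study will be referred to the DSMC for review of dosing and toxicity at the first occurrence of a toxic death".

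Rule B then counts toxicity-events, which is the 13.3(c) term. Its first stage reads "Stage 1: Accrue 7 evaluable participants. If at any time 2 or more participants experience a toxicity-event, enrollment will be suspended". The limit is 3 of 15 at the second stage and 7 of 25 at the third. Section 13.6 uses Rule B to address objectives 1.4.b (feasibility and toxicity) and 1.4.c.

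Section 10 requires that adverse events "within 30 days of the last study intervention need to be captured", and Section 10.1 requires an attribution for each.

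**The concern.** Rule B is the plan's only numeric toxicity rule, and the feasibility conclusion rests on it. It should be possible to say of any participant whether he or she counts. The documents do not allow that for some of the most serious outcomes. The 13.3(c) event depends on a decision to stop the drug. Once the last planned dose has been given there is nothing left to stop, and a death between cycles is not obviously a decision to stop. The 13.5 definition would catch both, but the plan never says that it defines the Rule B event. Two analysts could therefore report different event counts from the same data, at limits where one participant matters.

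**Working it through.** **1. The plan's own figures.** Inputs from Section 13.5: continue if at most 1 of 7 have events, continue if at most 2 of 15 (cumulative), declare tolerable if at most 6 of 25 (cumulative). With b(n,k) the binomial probability at true event rate p:

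P(tolerable) = Σ over x = 0..1, y = 0..2−x, w = 0..6−x−y of b(7,x)·b(8,y)·b(10,w)

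| True rate | Pass stage 1 | Pass stages 1 and 2 | Declared tolerable | Stated |
|---|---|---|---|---|
| 5% | 0.956 | 0.937 | 0.937 | 0.94 |
| 30% | 0.329 | 0.109 | 0.096 | 0.1 |

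The stated figures are right. They take the event as given, so they say nothing about who is counted.

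**2. The two definitions side by side.**

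| Situation | 13.3(c) toxicity-event | 13.5 unacceptable toxicity |
|---|---|---|
| Related death after completing therapy | Tolerated | Yes (grade 5) |
| Related death between cycles | No category | Yes (grade 5) |
| Related second malignancy, drug not stopped for toxicity concerns | Tolerated, or no category, depending on how far the word unrelated reaches | Yes if grade 5 or grade 3–4 non-hematological |
| Related, non-exempt grade 3–4 non-hematological toxicity, dosing held and resumed (6.3.2), all cycles given | Tolerated, if a hold is not a stop | Yes |
| Drug stopped for non-fatal prolonged cytopenia (6.3.1) | Event | No (hematological) |

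The definitions disagree in both directions, so neither contains the other.

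**3. Deaths after the last dose of Cycle 6.** Section 5 gives clofarabine on Days 1–5, so the last dose is on Day 5. Adverse events are captured for 30 days after it, to Day 5 + 30 = Day 35. Section 8 sets the off-treatment date at Day 28 of the last cycle.

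- If completion means the last dose, a related death on Days 6–35 is scored as tolerated.
- If completion means Day 28, a related death on Days 6–28 has no category and one on Days 29–35 is scored as tolerated.

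On neither reading does 13.3(c), taken literally, make it an event.

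**4. What one participant can do.** With 2 true events among the first 7, missing one leaves 1 and the trial proceeds. With 3 among 15, missing one leaves 2 and it proceeds. With 7 among 25, missing one leaves 6 and therapy is declared feasible. The stage 1 count equals exactly 2 with probability 21 × 0.3² × 0.7⁵ = 21 × 0.09 × 0.16807 = 0.318 at a true rate of 30%. That is how often the count sits on the limit from events of any kind; it is not the frequency of late deaths or second malignancies.

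**The case against.** The strongest reply is that 13.5 already covers this. Its definition of unacceptable toxicity stands in the paragraph that leads into Rule B, includes grade 5, and makes no exception for completers. On that reading a toxic death after Cycle 6 is an event. This stands to the extent that a reader should not infer that such deaths are definitely successes in Rule B. But Rule B uses the other term, and nothing equates the two.

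Second, toxic deaths are not overlooked. The first one goes to the DSMC, one event earlier than Rule B's first limit, and 13.6 tabulates grade 3 and higher toxicity (13.3(d) lists only grades 3–4). This also stands. However, the referral does not by itself suspend enrolment or add the death to Rule B's count or to the feasibility proportion.

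Third, for a non-fatal toxicity, scoring a participant who received every planned cycle as a success fits an endpoint about delivering therapy as planned. That is a legitimate design choice, provided it is stated.

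Fourth, a reader might infer that every second malignancy is a success. The documents do not support that. The opening word of the success sentence gives precedence to stopping for toxicity, and the words on relatedness can be read as covering both second malignancy and death. Nor does the remark in Section 2.1 that longer treatment is limited by myelosuppression "causing a clinical picture similar to myelodysplasia" strengthen the case. It concerns cladribine, and it describes prolonged myelosuppression rather than a malignancy. In this trial, Section 6.3.1 takes participants off study if counts have not recovered by Day 42 without hematopoietic involvement, which would ordinarily be stopping for toxicity.

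**Conclusion.** The point holds as a gap in definition. Rule B's event is not uniquely defined. Under the only text that defines its term, a treatment-related death after completion is a success, a treatment-related death between cycles is unclassified, and the position of a related second malignancy is unclear.

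The affected cases are probably few, and the documents give no rate for them, so no shift in Rule B's pass probability is claimed. The consequence is that at 2 of 7, 3 of 15 or 7 of 25 one such participant can decide the outcome. It would be wrong to conclude that Rule B's operating characteristics are misstated or that toxic deaths escape review. The finding rests on reading 13.3(c) literally and on the absence of any link from 13.5. If the sponsor always meant the 13.5 definition to feed Rule B, what is missing is that statement. This should be corrected, because the feasibility conclusion depends on it.

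**What to change.** - State one event definition and use it in both 13.3(c) and 13.5, for Rule B and for the feasibility proportion. If the 13.5 definition is kept for another purpose, say what that purpose is.
- In 13.3(c), define completion of therapy, and state that a death possibly, probably or definitely related to clofarabine, from first dose to 30 days after the last dose, is a toxicity-event even if all cycles were given.
- Reword the success clause so that it covers removal for *second malignancy unrelated to protocol therapy, or death unrelated to protocol therapy*, and count a related second malignancy in the same window as a toxicity-event.

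The cost is a few sentences. The 30-day window and the attribution categories are already in Section 10, so no new data are needed, and Rule B's limits and stated probabilities do not change. The small downside is that the observed toxicity-event proportion may be slightly less favourable.

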13.4 Evaluability

To be evaluable for inclusion in the analysis of response and toxicity, a patient must be eligible and have received at least one dose of protocol therapy. All evaluable participants must be assessed for response and toxicity to treatment, even if there are major protocol treatment deviations. Each participant should be assigned a category of response according to section 9 of the protocol.

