4 REGISTRATION PROCEDURES

4.1 General Guidelines for DF/HCC Institutions

Institutions will register eligible participants in the Clinical Trials Management System (CTMS) OnCore. Registrations must occur prior to the initiation of protocol therapy.

An investigator will confirm eligibility criteria and will complete and sign the protocol-specific eligibility checklist.

Following registration, participants may begin protocol therapy and should begin protocol therapy within 7 days. Issues that would cause treatment delays should be discussed with the Overall Principal Investigator (PI). If a participant does not receive protocol therapy following registration, the participant's registration on the study must be canceled. Registration cancellations must be made in OnCore as soon as possible.

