13.2 Sample Size/Accrual Rate

Twenty evaluable participants in Stratum 1 will be required in order to have sufficient power to address the study's primary objective. To account for participants who enroll and are subsequently determined to be ineligible or unevaluable, a total of up to 25 participants may be enrolled in order to obtain 20 evaluable patients. At an estimated accrual rate of 10 participants per year, the accrual goal of 20 evaluable participants can be achieved in less than 4 years. It is estimated that up to 10 patients per year meeting the eligibility criteria for Stratum 2 are seen across all study sites (personal communication from [name]). Therefore, the estimated accrual rate of Stratum 2 patients is up to 5 patients per year, which allows for up to 20 patients in Stratum 2, though realistically, fewer of these rare patients are anticipated to be enrolled. We estimate a total study accrual of up to 45 patients (25 in Stratum 1, and 20 in Stratum 2).

Once the accrual goal of eligible patients for a given stratum is reached (with a 5-patient overage to account for potentially ineligible patients), that stratum will be closed to accrual. Once the accrual goal of evaluable patients is met within Stratum 1, the overall study will be closed even if fewer than 20 patients have been enrolled in Stratum 2. In the unlikely event that 20 patients are enrolled on Stratum 2 before Stratum 1 has met its accrual goal, Stratum 2 will be closed to accrual.

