13.6 Statistical Methods to Address Objectives

Objective 1.3 - Monitoring Rule A will be used to address primary objective 1.3. The analysis will include all evaluable Stratum 1 participants. In addition, a 95% confidence interval will be placed on the response rate.

Secondary Objective 1.4.a – Descriptive analyses using the methods of Kaplan and Meier (with standard errors per Peto) will be performed to calculate the PFS and OS within each stratum and overall. Lifetables will also be constructed.

Secondary Objective 1.4.b – Monitoring Rule B will be used to address secondary objectives 1.4.b and 1.4.c. In addition, a descriptive tabulation of the proportion of participants reporting grade 3 and higher toxicity, separately by stratum (1 and 2) and by CTC toxicity code, will be generated for all evaluable patients. A given participant will be counted only one time per toxicity code at the maximum grade regardless of the number of times that participant experienced the toxicity.

Secondary Objective 1.4.c – Within Stratum 2 and within subgroups of Stratum 2, we will calculate the proportion of evaluable patients who are responders, and place 95% confidence intervals on these proportions. A descriptive tabulation of the proportion of participants reporting grade 3 and higher toxicity, by CTC toxicity code, will be generated for Stratum 2 patients. A given participant will be counted only one time per toxicity code at the maximum grade regardless of the number of times that participant experienced the toxicity.

CONFIDENTIAL

This document is confidential. Do not disclose or use except as authorized.

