17.5.1.5 Monitoring

The Participating Institutions will be required to submit participant source documents to the Coordinating Center for monitoring. Participating Institution may also be subject to on-site monitoring conducted by the Coordinating Center.

The Coordinating Center will implement ongoing monitoring activities to ensure that Participating Institutions are complying with regulatory and protocol requirements, data quality, and participant safety. Monitoring will occur before the clinical phase of the protocol begins, continue during protocol performance and through study completion. Additional monitoring practices may include but are not limited to; source verification, review and analysis of the following: eligibility requirements of all participants, informed consent procedures, adverse events and all associated documentation, study drug administration/treatment, regulatory files, protocol deviations, pharmacy records, response

CONFIDENTIAL

This document is confidential. Do not disclose or use except as authorized.

assessments, and data management.

A study monitor will be available for monitoring all participating sites. All monitoring reports and ongoing progress reports for all participating sites will be provided to the DF/HCC Sponsor. Any major monitoring findings will be communicated to the DF/HCC Sponsor immediately.

Virtual Monitoring

The monitor will be responsible for on-going virtual monitoring of regulatory documents and data entered by participating sites. Participating sites will be responsible for providing necessary source documentation for virtual monitoring.

All eligibility source documentation from all participating sites will be reviewed by the Coordinating Center prior to registering participants on protocol. At the time of registration, all points of eligibility must be found in either source documentation or if eligibility points cannot be found in source documentation (i.e. lab reports etc.), **they must be included in an MD note.**

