Registration documents (consent form and eligibility checklist) will also be reviewed via virtual monitoring at the time of registration. At the time of registration, the eligibility checklist(s) and all pages of the consent form(s) must be faxed or emailed to the DFCI Study Team for review (refer to protocol section 4 for participant registration process). The DFCI Study Team will review each consent form to ensure 1) it is the most appropriate and current version, 2) that the participant information is included on all pages of the consent and that all pages of the consent have been submitted, 3) that the participant has signed and dated the consent form, 4) that a physician has reviewed and signed the consent form on the same day/time as the participant, and that 5) all appropriate items have been completed.

Additional source documents that will be reviewed virtually include, but are not limited to:

- All results of the Required Assessments (Protocol Table 2).
- Any extra source documentation (i.e. admission notes, scans, culture results) pertaining to a serious adverse event (SAE).

In addition to enrollment documents, a subset of participants will have all data reviewed via virtual monitoring. This will occur once the participants complete cycle 1 of this study.

A list of items required to be virtually monitored will be provided to participating sites.

Virtual monitoring will be performed on an ongoing basis. The monitor will query within the Electronic Data Capture system. The DF/HCC Sponsor will be notified on an ongoing basis on the status of virtual monitoring, including which patients and what data has been virtually monitored. As part of virtual monitoring, if any significant non-compliance (i.e. if a patient is ineligible) is found during virtual monitoring this will be reported to the DF/HCC Sponsor immediately.

CONFIDENTIAL

This document is confidential. Do not disclose or use except as authorized.

On-Site Monitoring

On-site monitoring may occur if sub-standard performance is discovered during virtual monitoring.

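### Section 13.4 makes eligibility a condition of the toxicity set, so a patient given clofarabine and later found ineligible is not counted in Rule B or the 1.4.b toxicity table (minor)

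*Combined protocol and SAP*

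**What the plan says.** - Section 13.4 gives a single condition: for "inclusion in the analysis of response and toxicity, a patient must be eligible and have received at least one dose of protocol therapy".
- Section 13.5 carries that set into the stopping rule: "The toxicity monitoring rule will be applied to the first 25 evaluable participants". The stages of Rule B accrue 7, 15 and 25 evaluable participants over both strata. Stage 1 reads: "If at any time 2 or more participants experience a toxicity-event, enrollment will be suspended", for DSMB review. Stage 2 suspends at 3 or more of 15. At stage 3, 7 or more of 25 counts against feasibility.
- Section 13.6 restricts the objective 1.4.b toxicity table in the same way: "separately by stratum (1 and 2) and by CTC toxicity code, will be generated for all evaluable patients".
- The protocol foresees that some patients will prove ineligible after entry. Section 13.2 allows for "participants who enroll and are subsequently determined to be ineligible or unevaluable", and section 17.5.1.5 sets out what happens "if any significant non-compliance (i.e. if a patient is ineligible) is found during virtual monitoring".
- Such cases should be uncommon. For outside sites, "All eligibility source documentation from all participating sites will be reviewed by the Coordinating Center prior to registering participants on protocol" (17.5.1.5). For DF/HCC sites, "An investigator will confirm eligibility criteria and will complete and sign the protocol-specific eligibility checklist" (4.1).

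**The concern.** Eligibility matters when judging efficacy in the target disease. It has no bearing on whether a dosed patient was harmed. A shared set takes out of the toxicity count some patients who were exposed to the drug.

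The early boundaries are low, at 2 of 7 and 3 of 15, so one uncounted event can decide whether enrollment is suspended. The omission might also not be neutral, because some eligibility rules screen for toxicity risk. Exclusion 8 in section 3.2 lists the same conditions that section 6.1.1 says another study excluded after hepatotoxicity findings. That link is indirect: the other study gave clofarabine with etoposide and cyclophosphamide to pediatric patients with acute leukemia, whereas this trial gives clofarabine alone for histiocytosis.

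**Working it through.** **The plan's own figures.** The inputs are the Rule B boundaries in 13.5: continue with at most 1 event in 7 and at most 2 in 15; feasible with at most 6 in 25. An exact three-stage binomial calculation gives:

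| True event rate | P(tolerable), recomputed | Stated |
|---|---|---|
| 5% | 0.937 | 0.94 |
| 30% | 0.096 | 0.1 |

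The stated figures are correct. They depend only on the stage sizes, the boundaries and the event rate, so they hold equally for a set of dosed patients with that rate.

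**Effect of leaving one patient out at stage 1.** The documents give no rate of dosed-but-ineligible patients, so the following is an assumption. Exactly one of the first seven dosed patients is ineligible and is replaced by an eligible one. Eligible patients have event rate p and the ineligible patient has rate r. The replacement changes the stage 1 result only if exactly one of the six eligible patients has an event, which has probability A = 6p(1−p)^5.

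- Missed suspension (ineligible patient has an event, replacement does not): r × A × (1−p)
- Extra suspension (ineligible patient has none, replacement does): (1−r) × A × p
- Difference: A × (r − p)

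With r = p, missed and extra are both 6p²(1−p)^6 and the difference is zero. With r = 2p the difference is A × p.

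| p | A | Missed = extra, r = p | Missed, r = 2p | Extra, r = 2p | Net loss, r = 2p |
|---|---|---|---|---|---|
| 5% | 0.2321 | 1.1% | 2.2% | 1.0% | 1.2 points |
| 10% | 0.3543 | 3.2% | 6.4% | 2.8% | 3.5 points |
| 20% | 0.3932 | 6.3% | 12.6% | 4.7% | 7.9 points |
| 30% | 0.3025 | 6.4% | 12.7% | 3.6% | 9.1 points |

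For example, at p = 0.20 and r = 0.40, missed = 0.40 × 0.3932 × 0.80 = 0.126 and extra = 0.60 × 0.3932 × 0.20 = 0.047.

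**Why the missed figures are upper bounds.**

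- They assume that ineligibility is established before the deciding event. Until then the patient is counted as evaluable, and Rule B can suspend at any time.
- A miss at stage 1 is not final. It leaves exactly one event among the seven evaluable patients, and stage 2 suspends if two or more of the next eight have an event. That probability is 1 − (1−p)^8 − 8p(1−p)^7, which is 0.497 at p = 0.20 and 0.745 at p = 0.30. About 50% and 74% of the misses are therefore still caught.

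**Cost of counting all dosed patients.** Assume 5% of dosed patients are ineligible and have an event rate of 20%, against 10% in the rest. The mixed rate is 0.95 × 0.10 + 0.05 × 0.20 = 0.105. The chance of suspension by patient 15 is then 0.258, against 0.237 at a rate of 0.10.

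**The case against.** Rule B asks whether therapy can be delivered as planned, which is a secondary objective. Judging that in eligible, treated patients is a defensible choice, and no stated figure is wrong. That stands, and it is why this is an improvement to the plan and not the correction of an error.

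Protection outside Rule B also stands. Adverse events are captured from the first dose (section 10), the DSMC reviews toxicity (11.2), and a toxic death triggers referral (13.5). Eligibility exceptions need IRB approval (17.3.7.2), and the laboratory criteria must be met again before every cycle (5.1, 5.2). Stages 1 and 2 suspend for review; they do not end the trial. However, none of these is a numerical trigger for non-fatal toxicity.

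It can also be said that the suspension sentence refers to participants without the word evaluable, and that the 1.4.c table in 13.6 is for Stratum 2 patients without that word. But 13.5 fixes Rule B's population as evaluable, and 13.4 governs the toxicity analysis generally. If all dosed patients were intended, the text still needs to say so.

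A reader might infer that the rule is biased toward finding the drug tolerable. The documents do not support this. With equal event rates the missed and extra suspensions cancel, no passage gives an event rate for ineligible patients, and many eligibility failures, such as the prior-regimen requirement, have no evident link to toxicity.

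**Conclusion.** The point holds as a minor one. Read together, 13.4, 13.5 and 13.6 leave a dosed patient who is later found ineligible out of Rule B and the 1.4.b table.

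The consequence depends on an unknown. If such patients have the same event rate as the rest, individual trials may be suspended or not on a different patient's result, but average operating characteristics do not change. There is a net loss of sensitivity only if their rate is higher. The doubled rate used above is an illustration with no source in the documents, as is the assumption of one such patient in the first seven. The 13.2 overage of 5 in 25 is a ceiling and not an estimate, since it also covers unevaluable patients who may never be dosed.

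One editorial note: 13.5 defines unacceptable toxicity by grade, attribution and exceptions directly before Rule B, and the term is not used again. A reader might infer that Rule B's event is ambiguous or that its probabilities refer to the wrong event. The text does not bear that out: Rule B counts toxicity-events, which 13.3(c) defines, and no stated figure is affected.

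**What to change.** In 13.4, separate the two sets. Response keeps the condition of being eligible with at least one dose. Toxicity, Rule B and the 1.4.b table take all patients with at least one dose. Align the wording of 13.5 and 13.6. As tidying, reconcile 13.3(c), 13.5 and Rule B by linking the definition of unacceptable toxicity to a stated use or deleting it; the choice is the sponsor's.

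The cost is a short text amendment, with no added patients or visits and no change to the boundaries or to the stated 0.94 and 0.1. The toxicity and response sets may differ slightly, and an event in a patient outside the target population could prompt a review. In the example above, that moves the chance of suspension by patient 15 from 0.24 to 0.26. The DSMB can weigh the ineligibility at that review.
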